NATIONAL AND KAPODISTRIAN UNIVERSITY OF ATHENS

DEPARTMENT OF MEDICINE

01 July 2021

STUDY TITLE

Effects of IL17/23 inhibitors on markers of subclinical atherosclerosis in patients with psoriasis: an observational study

STUDY PROTOCOL

Introduction

Plaque psoriasis is a chronic inflammatory disease characterized by the development of clearly demarcated, erythematous, pruritic plaques on the skin of genetically predisposed individuals. It has a worldwide incidence of 0.5–11%, with over 50% of patients developing the disease in the first three decades of life. In recent years, increasing evidence supports that psoriasis is a systemic inflammatory disease that extends beyond the skin, as it is often associated with comorbidities, including psoriatic arthritis, cardiovascular disease, metabolic syndrome, and inflammatory bowel disease, greatly affecting the quality of life of patients and mortality (1).

The pathophysiology of psoriasis is complex and has been shown to be due to inflammatory mediators of the Th1 and Th17 immune response, such as tumor necrosis factor (TNF- α), interleukin (IL) 1, IL6, IL12, IL17A, IL17F and IL23. In fact, it has been shown that these pathways are shared between psoriasis and the aforementioned comorbidities and, thus, their selective inhibition with newer biological therapies positively affects this entire disease spectrum beyond the skin (1). Regarding cardiovascular disease, current data support that psoriasis is an independent cardiovascular risk factor, as systemic inflammation can also affect the vascular endothelium in addition to the skin (2). Therefore, understanding the common pathophysiological mechanisms between psoriasis and atherosclerosis as well as studying the effect of newer biologic agents approved for the treatment of moderate/severe psoriasis on atherosclerosis may contribute to optimal management of these patients. The present study aims to highlight the effect of IL23/IL17 pathway inhibition on subclinical atherosclerosis in patients with moderate-to-severe psoriasis.

Background

Increasing evidence supports the importance of the Th17 immune response in the pathogenesis of psoriasis (3–5). Th17-differentiated T cells produce large amounts of IL17 (particularly the IL17A and IL17F isoforms), a cytokine that is significantly involved in local skin immune mechanisms and the inflammatory process of psoriasis. It has been shown that Th17 (as well as Th1) cells are found in the dermis of psoriatic lesions and produce IL17 and IL22, which in turn promote the secretion of inflammatory and antimicrobial molecules by keratinocytes. Another important cytokine is IL23, which is

responsible for the survival and expansion of Th17 cells and IL17 production (4). In combination with the above, the development of new biological agents against IL17 and IL23 for the treatment of psoriasis has highlighted *in vivo* the essential role of the IL23/Th17 axis in its pathogenesis (6).

Interestingly, the same axis has also been shown to play an important role in the pathophysiology of atherosclerosis (2,7). In one study, increased levels of IL23 and its receptor (IL23R) have been found in the blood and atherosclerotic plaque of patients with carotid atherosclerosis compared with healthy volunteers. Another study showed that both psoriasis patients and those with acute coronary syndrome have increased levels of Th17 immune response cytokines in the blood, including IL17A (8). The increased levels of IL17A in these patients have been correlated with the degree of platelet aggregation measured *in vitro*, suggesting that IL17A may promote platelet aggregation in acute coronary syndrome (9).

Taking into account the above data, it has been hypothesized that inhibition of the IL23/Th17 axis may lead to simultaneous improvement of psoriatic and concomitant atherosclerotic disease (1). To date, isolated studies have shown this association in patients receiving IL17 inhibitors for moderate or severe psoriasis. Specifically, in one study, treatment of patient for one year with an IL17 inhibitor (secukinumab) resulted in improvements in myocardial deformation, arterial elasticity, and coronary artery function, along with significant reductions in psoriasis activity and oxidative stress, findings that were not observed in patients treated with cyclosporine or methotrexate (10). In contrast, another study of patients with psoriasis did not demonstrate a significant benefit in terms of cardiovascular risk in patients treated with IL23/Th17 axis inhibitors (ustekinumab, secukinumab, ixekizumab), which was partly attributed to the short duration of treatment and follow-up (6 months) (11). Finally, in another study, biological therapy with TNF- α , IL17, and IL12/23 inhibitors was associated with reduced coronary inflammation assessed by the perivascular fat attenuation index (12).

Outcomes

The primary outcome is the assessment of the effect of treatment with an IL17 or an IL23 inhibitor on arterial stiffness in patients with moderate-to-severe psoriasis, by evaluating the pulse wave velocity (PWV) and the augmentation index normalized to 75 beats/min (Alx75) at baseline, after 24 and 52 weeks of treatment. Secondary outcomes were the comparison of change in PWV and Alx75 between the study groups and the assessment of change in psoriasis disease severity scores and in ankle-brachial index (ABI)

Patients

This observational cohort study was performed between September 2021 and September 2024. Consecutive patients with plaque psoriasis with or without psoriatic arthritis, who were monitored in the outpatient department of a tertiary academic hospital for skin diseases were included in the study if they fulfilled all of the following inclusion criteria: 1. Age \geq 18 years; 2. Clinical diagnosis of moderate-to-severe psoriasis (Psoriasis Area Severity Index (PASI) score > 10 or Body Surface Area (BSA) >10 or Dermatology Life Quality Index (DLQI) >10); 3. Treatment with an IL17 inhibitor [secukinumab (Cosentyx[®]), ixekizumab (Taltz[®]), brodalumab (Kyntheum[®])] or an IL23 inhibitor [risankizumab (Skyrizi[®]), guselkumab (Tremfya[®])] or a conventional systemic agent (e.g. methotrexate, cyclosporine) or a small molecule [apremilast (Otezla[®])] as monotherapy for a total of 52 weeks. The exact agent was chosen from the treatment physician of each patient, based on disease characteristics and comorbidities. Patients who did not receive biologic therapy served as a control group. Patients were not included in the if they fulfilled any of the following criteria: 1. Prior therapy with an IL17 or IL23 inhibitor; 2. Prior therapy with an TNFa-inhibitor for up to 3 months before entering the study; 3. Chronic or severe acute infections, malignancy, pregnancy or lactation

Study location

The study will be conducted at the First University Dermatology Clinic of the National and Kapodistrian University of Athens, at the "Andreas Syggros" Hospital of Athens, in

collaboration with the First University Cardiology Clinic of the National and Kapodistrian University of Athens, at the "Hippokratio" Hospital of Athens.

Materials and Methods

The enrollment of patients who will participate in the study will be carried out at the psoriasis clinic of the "Andreas Syggros" Hospital in Athens. All patients will provide written informed consent prior to enrollment in the study. The selection and administration of the biological agent will be done according to the usual practices of the psoriasis clinic based on the characteristics of the patient/disease and the international guidelines for the administration of each drug. Assessment of psoriatic disease and evaluation response will take place before the start of treatment, at week 24 and 52.

Monitoring of psoriasis

Psoriasis assessment scores including Psoriasis Area Severity Index (PASI), physician global assessment (PGA), Body Surface Area (BSA) and Dermatology Life Quality Index (DLQI) were assessed at baseline, after 24 and 52 weeks of treatment.

Monitoring of cardiovascular parameters

All patients will undergo measurement of carotid-femoral PWV, Alx75 and right and left ABI at baseline, after 24 and 52 weeks of treatment.

Statistical analysis

Statistical analysis will be performed using Statistical Package for the Social Sciences for iOS (version 29.0.2.2 IBM Corp: Armonk, NY, USA). Descriptive statistics will be used to present the patients' characteristics. Variables with normal distribution will be reported as mean \pm standard deviation (SD), while not normally distributed outcomes will be reported as median values and range. Categorical variables will be presented as frequencies and percentages. Between-group analysis will be performed using the Kruskal-Wallis Test and Student's t-test or one-way ANOVA test. Statistical significance is determined at a two-tailed p value of 5% (0.05).

Funding

The biological agents that will be administered are approved for the treatment of moderate/severe psoriasis in Greece, so the cost of treatment will be covered by each patient's insurance after electronic prescription of each drug. The laboratory test that will be performed is part of the usual practice of monitoring treatment with biological agents, so the costs will be covered by the patient's insurance, after electronic prescription. There will be no external funding for the study.

Principal investigator

[name]

Subinvestigators

[name]

[name]

[name]

[name]

[name]

[name]

[name]

[name]

[name]

[name]

[name]

References

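### The primary outcome is an effect of treatment with no comparator and no matching test; effect claims should rest on the contrast with the concurrent non-biologic controls, now listed as secondary

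*Combined protocol and SAP*

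**What the plan says.** The Introduction gives the aim: "The present study aims to highlight the effect of IL23/IL17 pathway inhibition on subclinical atherosclerosis in patients with moderate-to-severe psoriasis".

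Under Outcomes, "The primary outcome is the assessment of the effect of treatment with an IL17 or an IL23 inhibitor on arterial stiffness", judged by PWV and AIx75 at baseline and weeks 24 and 52. The sentence names neither a comparator nor a summary measure. The next sentence adds: "Secondary outcomes were the comparison of change in PWV and Alx75 between the study groups".

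Under Patients, the treatments listed are IL17 inhibitors, IL23 inhibitors, conventional systemic agents and apremilast, each "as monotherapy for a total of 52 weeks". Then: "Patients who did not receive biologic therapy served as a control group". On allocation: "The exact agent was chosen from the treatment physician of each patient, based on disease characteristics and comorbidities".

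Under Monitoring of cardiovascular parameters, every patient, controls included, has PWV, AIx75 and ABI measured at the same three visits.

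Under Statistical analysis, the only inferential methods are the Kruskal-Wallis test, Student's t-test and one-way ANOVA, all labelled as between-group. None is assigned to an outcome. No paired, repeated-measures or baseline-adjusted method appears.

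**The concern.** The study is meant to speak about an effect of pathway inhibition. As written, its headline result can be a before-after change in treated patients, while the comparison that could test whether that change differs from change on other systemic treatment sits among the secondary outcomes. If the two disagree, the plan does not say which one carries the claim.

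A change within one arm mixes any drug effect with everything else that moves over 52 weeks. Ageing would tend to push stiffness up and so hide a benefit. Other influences, such as changes in co-medication or in measurement, could push either way; the documents describe none of them. A concurrent group measured at the same visits removes whatever part of this is common to all groups. That group exists here, but the primary outcome does not use it.

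**Working it through.** **1. Two readings of the primary outcome, set against the rest of the plan**

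| Reading | Fits the listing of secondary outcomes? | Has a named test? | Supports an effect claim? |
|---|---|---|---|
| Change within treated patients | Yes, it is distinct from the between-group comparison | No, all named tests are between-group | No, shared time trends are included |
| Contrast with the control group | No, it repeats the secondary comparison for the inhibitor groups | Yes | As an association only |

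The first reading is the more natural because the between-group comparison is listed separately. Each reading leaves a gap, and neither gap depends on a missing figure.

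**2. Can the contrast be computed from what is planned?** Yes. Controls are designated (Patients), are measured at the same visits (Monitoring of cardiovascular parameters), and a comparison of change is already planned (Outcomes). Baseline PWV, AIx75 and PASI are collected, and age is known from eligibility.

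**3. Illustration of shared drift.** The plan states no figure that can be reproduced; its only numerical input is two-sided alpha 0.05. The assumptions are no drug effect, a drift of d SDs of the change score, and n patients per group.

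- Within-arm paired t-test: noncentral t, df = n − 1, noncentrality d√n.
- Between-group t-test when the groups' drifts differ by d: df = 2n − 2, noncentrality d√(n/2).

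| d | n | Within-arm rejection (two-sided) | Between-group, shared drift | Between-group, drifts differ by d |
|---|---|---|---|---|
| 0.2 | 20 | 13.6% | 5% | 9.5% |
| 0.2 | 40 | 23.5% | 5% | 14.3% |
| 0.2 | 60 | 33.2% | 5% | 19.2% |
| 0.3 | 20 | 24.7% | 5% | 15.2% |
| 0.3 | 40 | 45.7% | 5% | 26.3% |
| 0.3 | 60 | 62.8% | 5% | 37.1% |

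Nearly all of the within-arm rejections lie in the direction of the drift. If the drift is upward, as with ageing, the chance of a significant fall in stiffness is at most 0.25% (d = 0.2, n = 20), against a nominal 2.5%. The error is then a masked benefit or an apparent worsening. The documents show no source of downward drift.

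**4. Precision lost by using the contrast.** With k treated patients per control and baseline-to-follow-up correlation r (both assumed), the SE relative to the treated arm's own change is √(1 + k) unadjusted and √((1 + k)(1 + r)/2) with baseline adjustment.

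- k = 1: √2 = 1.41 unadjusted; √1.5 = 1.22 (r = 0.5) to √1.8 = 1.34 (r = 0.8) adjusted.
- k = 2: √3 = 1.73 unadjusted; √2.25 = 1.50 to √2.7 = 1.64 adjusted.

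Covariates that differ between groups cost some further precision.

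**The case against.** The strongest reply is that the design is labelled observational, the control group and the comparison of change are already planned, and the contrast is itself confounded because physicians chose the agent on disease characteristics and comorbidities. The right-hand column in the working shows that unequal drift also inflates the between-group test, and nothing in the documents bounds that inequality. Controls are on active systemic drugs, so the contrast also answers a different question from change on treatment. In non-randomised groups, baseline adjustment and a comparison of change can give different answers, and neither is settled as correct.

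Much of this stands. It limits what the contrast can claim and is why both analyses should be shown. It does not make an uncontrolled change a better basis, since that change carries the shared trends as well.

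Several stronger inferences are tempting and should not be drawn:

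- *That 14% to 63% is the risk of falsely claiming vascular improvement.* It is two-sided, rests on assumed drift, and the one directional drift identified works against a benefit.
- *That independent-sample tests will be run across visits.* The plan labels them between-group and does not propose this. The gap is that no within-patient method is named.
- *That the study lacks a control group or leaves its groups undefined.* The Patients section lists the drug classes and designates the controls. What is open is whether IL17 and IL23 inhibitors are pooled.
- *That the supporting study proves a formal contrast is needed.* The Background reports "findings that were not observed in patients treated with cyclosporine or methotrexate", which points to a comparison with non-biologic treatment. It does not say whether the groups were tested against each other.

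**Conclusion.** The concern holds as a fault in the primary outcome: it promises an effect, names no comparator, and has no matching analysis on its most natural reading. A usable concurrent contrast is ranked below it. This should be fixed, because it decides which result carries the study's main claim.

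The textual finding needs no assumptions. Its numerical size cannot be fixed from the documents; the drift and precision figures are illustrations over assumed n, drift, correlation and group ratio. A reader might infer that moving to the contrast yields a causal effect of the inhibitors. It does not. It supports an association relative to non-biologic systemic treatment, with confounding by physician choice still present. Selection on completing 52 weeks of monotherapy affects every group, may differ between them, and is not repaired by the contrast.

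**What to change.** Reword the primary outcome along these lines: *the difference in change from baseline in PWV and in AIx75, at weeks 24 and 52, between patients treated with an IL17 or IL23 inhibitor and the concurrent non-biologic control group; any claim of an effect on arterial stiffness rests on this difference.* Also:

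- State whether IL17 and IL23 inhibitors are each compared with control or pooled.
- In Statistical analysis, name a linear model adjusted for the baseline value of the outcome, age, baseline PASI and any comorbidities recorded at baseline. Show the unadjusted comparison of change beside it.
- Report within-group change descriptively, with 95% confidence intervals from a paired or repeated-measures method, and do not use it alone to claim a treatment effect.
- Word the result as an association relative to non-biologic systemic treatment. List physician choice of agent and selection on 52 weeks of monotherapy as limitations.
- The protocol is dated 01 July 2021, yet Patients says "This observational cohort study was performed between September 2021 and September 2024". If outcome data have been seen, date and disclose the change, and report the primary outcome as now worded alongside.

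The cost is text in two sections, with no new visits or measurements. The downside is the loss of precision shown above and the confounding that remains. Multiplicity across two measures and two time points is a separate matter that this change does not settle.

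### Agents are chosen on disease characteristics and comorbidities, but the secondary between-group comparison of change in PWV and AIx75 is planned only with unadjusted tests, leaving it open to confounding by indication

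*Combined protocol and SAP*

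**What the plan says.** All references are to the combined protocol and SAP.

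- **Patients**, on treatment assignment: "The exact agent was chosen from the treatment physician of each patient, based on disease characteristics and comorbidities". On the comparator: "Patients who did not receive biologic therapy served as a control group". These are patients on a conventional systemic agent or apremilast.
- **Patients**, exclusions: besides certain earlier biologic treatment, the list is "Chronic or severe acute infections, malignancy, pregnancy or lactation". No cardiometabolic condition is excluded, and patients may enter with or without psoriatic arthritis.
- **Outcomes**: "Secondary outcomes were the comparison of change in PWV and Alx75 between the study groups". The primary outcome is worded differently, as the effect of an IL17 or IL23 inhibitor on PWV and AIx75 assessed at baseline and weeks 24 and 52.
- **Statistical analysis**: "Between-group analysis will be performed using the Kruskal-Wallis Test and Student's t-test or one-way ANOVA test". On patient characteristics: "Descriptive statistics will be used to present the patients' characteristics". Significance is two-sided at 5%.
- **Introduction**, on psoriasis: "it is often associated with comorbidities, including psoriatic arthritis, cardiovascular disease, metabolic syndrome, and inflammatory bowel disease". On mechanism: "these pathways are shared between psoriasis and the aforementioned comorbidities".

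The documents contain no covariate-adjusted model, propensity score, weighting, matching or stratification, and no list of confounders. They also give no sample size, SD or expected effect.

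**The concern.** The protocol names what drives treatment choice, and the analysis then takes no account of it. None of the three named tests takes a covariate. If a factor that guides the choice of agent also predicts the 24- or 52-week change in PWV or AIx75, the difference between groups mixes drug effect with patient mix. Recruiting more patients does not shrink that bias. It only makes a false difference more likely to reach significance.

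This matters because the comparison with the non-biologic group is the protocol's only contrast with concurrent patients who are not on an IL17 or IL23 inhibitor. It is the natural place for a reader to look for evidence that a change seen on a biologic is due to the biologic.

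**Working it through.** The plan states no figure that can be reproduced here, so the check has two parts: a reading of the text, and an illustration on assumed values.

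**1. The text side by side.** Comorbidity is a stated driver of treatment choice (Patients). The Introduction lists cardiovascular disease, metabolic syndrome and psoriatic arthritis among the comorbidities and ties them to psoriasis through common inflammatory pathways. The exclusions leave these patients in the study. The named tests ignore them (Statistical analysis). Confounding is therefore plausible. The missing link is that no passage says a comorbidity predicts *change* in PWV or AIx75.

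**2. False-positive rate of the unadjusted test.** Assumed, not in the documents: two groups of n each, no true effect, and a confounding bias b in SDs of change. From the plan: two-sided 5%.

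For a yes/no comorbidity, b = (difference in prevalence) × (difference in change between patients with and without it):
- 35% v 45%, 0.5 SD: 0.10 × 0.5 = 0.05
- 30% v 60%, 0.5 SD: 0.30 × 0.5 = 0.15
- 25% v 65%, 0.8 SD: 0.40 × 0.8 = 0.32

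The t statistic is noncentral t with 2n − 2 degrees of freedom and noncentrality b√(n/2). For b = 0.32 and n = 80 this is 0.32 × √40 = 2.02. Rejection rates:

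| b (SD) | n = 20 | n = 30 | n = 50 | n = 80 |
|---|---|---|---|---|
| 0.05 | 5.3% | 5.4% | 5.7% | 6.1% |
| 0.15 | 7.5% | 8.8% | 11.5% | 15.6% |
| 0.32 | 16.7% | 23.0% | 35.4% | 52.1% |

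**3. What adjustment does in the same cases.** Change was simulated (20,000 runs per case) and regressed on group, age, baseline PASI, comorbidity and psoriatic arthritis. Only comorbidity was imbalanced and related to change.
- Comorbidity measured perfectly: bias 0.00, rejection 4.8 to 5.3%, standard error 0.99 to 1.09 times the unadjusted one. The zero bias is built in, because the only confounder is a covariate in the model.
- Comorbidity left out: the full bias stays, with rejection 5.0 to 51.2%.
- Comorbidity recorded with sensitivity 0.80 and specificity 0.95 (assumed): bias of about 0.02, 0.065 and 0.145 SD remains, with rejection 4.9 to 15.1%.

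**4. Should the baseline value of the outcome be in the model?** Assume a test-retest correlation of 0.7 and no effect. The SD of change is then √(2 × (1 − 0.7)) = √0.6 = 0.775 level SD.
- Stable group difference of 0.5 level SD: the change model has bias 0. Adding baseline gives (1 − 0.7) × 0.5 = 0.15 level SD, or 0.15/0.775 = 0.19 SD of change.
- Treatment selected on the observed baseline value, giving the same 0.5 difference: the change model is off by 0.19 SD of change in absolute size. Adding baseline gives 0.

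Each model is biased by about 0.19 SD under the other's assumption, which is more than the middle case of 0.15 SD in step 2.

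**The case against.** Four arguments can be made for the plan.

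*The comparison is secondary, and the study is labelled observational.* Both are true, and both limit the weight of the point. But the label adjusts nothing, and the plan applies a 5% significance threshold with no caveat about confounding.

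*Change scores already deal with group differences.* They do so for stable differences in level only.

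*The evidence stops short of bias.* This stands. A reader might infer that the groups will be imbalanced, that comorbidity drives change in arterial stiffness, or that the comparison will be biased in favour of the biologics. The documents support none of these. They show a stated driver of treatment choice with no provision for it in the analysis.

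*Any particular covariate list or model is a matter of preference.* This stands in part. The Introduction also names inflammatory bowel disease, so a list that omits it needs a reason. A category such as cardiometabolic comorbidity cannot be applied until it is defined. The documents do not say whether measured PWV or AIx75 influenced treatment choice, and that silence does not justify preferring the model without baseline. The fix leaves these points for the sponsor to settle before analysis.

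A smaller point also stands: the sentence on between-group analysis is not restricted to outcomes and could cover baseline characteristics too. Testing baseline differences would still not adjust for them.

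**Conclusion.** The point holds as a gap in the analysis plan that should be fixed. The secondary between-group comparison of change in PWV and AIx75 is open to confounding by indication, because choice of agent depends on patient characteristics that the named tests ignore.

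The absence of adjustment can be read directly from the documents. The size and direction of any bias cannot. The range of about 5% to about 52% rests entirely on assumed group sizes, imbalances and effects on change, for two groups and one confounder. It shows what could happen and does not predict what will.

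Two wider readings should be avoided. The point does not address the primary outcome, which is worded as an assessment over time on treatment. Nor does the illustration show that adjustment would remove confounding in practice, since that depends on measuring the right factors well.

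**What to change.** Add to the Statistical analysis section:

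> Change from baseline in PWV and AIx75 at weeks 24 and 52 is compared between groups (IL17 inhibitor, IL23 inhibitor, non-biologic control as reference) by linear regression, adjusted for age, baseline PASI, psoriatic arthritis (yes/no) and cardiometabolic comorbidity (yes/no, with the qualifying diagnoses listed before analysis). Any other comorbidity that the clinic uses to choose the agent, such as inflammatory bowel disease, is added to the list, or its omission is justified, before analysis. The model is fitted with and without the baseline value of the outcome. Which is main is fixed and justified before analysis according to whether baseline PWV or AIx75 informed treatment choice, and both are reported. Standardised baseline differences are tabulated by group. Unadjusted tests of these outcomes are descriptive, and between-group results are worded as associations.

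The three group levels are inferred from the agents listed under Patients, and the sponsor should confirm them.

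**Cost.** Plan wording and some analysis time. Age is needed for eligibility and PASI is a planned baseline assessment. Comorbidity and psoriatic arthritis status are not stated as recorded, so they may have to come from clinic records and may be incomplete or misclassified. In the illustrated cases the standard error rises by up to about 9% at 20 per group; it would rise more if other covariates were also imbalanced. Residual confounding remains, about 0.02 to 0.15 SD in the illustration with imperfectly recorded comorbidity, and the report should say so.

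### Earlier conventional systemic therapy is neither restricted at entry nor used in the analysis, so it can distort the change from baseline in PWV and AIx75

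*Combined protocol and SAP*

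**What the plan says.** All references are to the combined protocol and SAP.

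- **Exclusions (Patients).** The two that concern earlier treatment are "1. Prior therapy with an IL17 or IL23 inhibitor; 2. Prior therapy with an TNFa-inhibitor for up to 3 months before entering the study". I read the second as a limit on recent use, though its wording is loose. The remaining exclusion, "3. Chronic or severe acute infections, malignancy, pregnancy or lactation", does not concern earlier psoriasis drugs.
- **Control treatments (Patients).** Besides the biologics, patients may receive "or a conventional systemic agent (e.g. methotrexate, cyclosporine) or a small molecule", namely apremilast. The comparator is defined by "Patients who did not receive biologic therapy served as a control group".
- **Treatment rule (Patients).** Study treatment is given "as monotherapy for a total of 52 weeks".
- **Source population (Patients).** Consecutive patients "who were monitored in the outpatient department of a tertiary academic hospital for skin diseases". They need not be untreated.
- **Baseline timing.** Materials and Methods states: "Assessment of psoriatic disease and evaluation response will take place before the start of treatment, at week 24 and 52". Monitoring of cardiovascular parameters places PWV, AIx75 and ABI at baseline, week 24 and week 52, and defines no treatment-free interval.
- **Outcomes.** The effect of an IL17 or IL23 inhibitor on PWV and AIx75 over 52 weeks is primary. The comparison of change between groups is secondary.
- **Statistical analysis.** Kruskal-Wallis, t-test or one-way ANOVA, two-sided 5%. No covariate and no sensitivity analysis is named.

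**The concern.** Every result of this study is read against the baseline measurement. If a patient stops one systemic agent shortly before starting the study drug, the later change mixes the effect of the new drug with the fading of the old one. For the primary outcome this matters even when all groups have the same treatment history, because the change on IL17/IL23 inhibitors is judged from the patients' own baselines.

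The between-group comparison has a second weakness. The exclusions apply to everyone, so controls too must never have had an IL17 or IL23 inhibitor. But only in the biologic groups does this rule make patients new to the class they are about to start. A control patient may be restarting methotrexate, cyclosporine or apremilast. The treating physician chooses the agent from disease characteristics and comorbidities, so similar treatment histories across groups cannot be assumed. If the share of recently treated patients differs, the difference in change carries a spurious component that the planned tests can neither detect nor remove.

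**Working it through.** **Step 1. Does any other text close the gap?**

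- The monotherapy rule covers the 52 study weeks, not the time before baseline.
- Assessment before treatment starts fixes the order of assessment and study drug. It does not make the baseline free of earlier drugs.
- The activity criterion (PASI >10 or BSA >10 or DLQI >10) can be met on DLQI alone, and it says nothing about PWV or AIx75.
- The analysis section uses no variable for earlier therapy.

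The gap stands.

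**Step 2. Is there a figure to reproduce?** No. The documents give no sample size, SD, effect size or power. What follows is an illustration, and all its inputs except the 5% level are assumptions.

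**Step 3. Inputs.**

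| Input | Value | Source |
|---|---|---|
| Difference between groups in share recently exposed, d | 0 to 0.6 | assumption |
| Shift in baseline PWV from earlier therapy that later fades, c | 0 to 0.5 m/s | assumption |
| SD of change in PWV | 1.0 m/s | assumption |
| Patients per group, n | 30 to 50 | assumption |
| Significance level | 0.05, two-sided | Statistical analysis |

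**Step 4. Spurious difference in change.** b = d × c.

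- Lower end: 0, if either d or c is 0.
- Small non-zero case: 0.2 × 0.3 = 0.06 m/s.
- Upper end: 0.6 × 0.5 = 0.30 m/s.

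**Step 5. False-positive rate of the between-group t-test.** With no true difference, the test statistic follows a non-central t distribution with 2n − 2 degrees of freedom and non-centrality b / (SD × √(2/n)). The standard error is 1.0 × √(2/30) = 0.258 m/s for n = 30 and 1.0 × √(2/50) = 0.200 m/s for n = 50.

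| b (m/s) | n = 30: non-centrality | rate | n = 50: non-centrality | rate |
|---|---|---|---|---|
| 0 | 0 | 5.0% | 0 | 5.0% |
| 0.06 | 0.23 | 5.6% | 0.30 | 6.0% |
| 0.15 | 0.58 | 8.8% | 0.75 | 11.5% |
| 0.30 | 1.16 | 20.8% | 1.50 | 31.8% |

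**Step 6. Within-group change.** Here the bias is the exposed share in that group times c, and it does not cancel when groups are alike. With shares of 0.2 to 0.6 and c from 0 to 0.5 m/s it runs from 0 to 0.6 × 0.5 = 0.30 m/s. Its sign depends on what the earlier agent did to arterial stiffness, which the documents do not settle.

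**The case against.** The strongest objection comes from the protocol itself. The Background describes a one-year study in which improved arterial elasticity was seen with secukinumab but not with cyclosporine or methotrexate. If those agents do not move arterial stiffness, stopping them should not either, and c is near zero. It is the only evidence in the document on these drugs and arterial function, and it is the reason the range in the working starts at zero. It remains one cited study, and the protocol reports nothing from it on apremilast.

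Second, patients must have active disease at entry, and psoriasis is assessed before treatment starts. This argues against controls simply continuing an established drug and limits carry-over in the skin scores. It stands in part: it does not rule out a restart or a switch, and it does not constrain the vascular measures.

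Third, the numbers are all assumed. That is correct. The 32% needs the largest imbalance, shift and group size together, and it concerns only the secondary test.

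Two stronger readings are tempting. A reader might infer that the baselines *are* distorted, or that the comparison is biased in favour of the biologics. The documents show only that distortion is possible, and give neither size nor direction. A reader might also infer that earlier ustekinumab is plainly allowed because the exclusions do not name it. The Background counts it among "IL23/Th17 axis inhibitors (ustekinumab, secukinumab, ixekizumab", and the first exclusion can be read as covering it. That is an ambiguity, not a demonstrated gap.

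**Conclusion.** The point holds as a possibility that the plan leaves unexamined. Followed as written, the protocol lets any patient's baseline follow recent conventional systemic therapy or apremilast, requires only the biologic groups to be new to their own class, and compares physician-chosen treatments without using treatment history.

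The primary within-patient change is exposed whatever the balance between groups. The secondary contrast is exposed only if recent treatment differs between them. Under the stated assumptions the false-positive rate of the secondary test lies between 5% (no carry-over, or equal exposure) and 32%. That range does not separate a negligible problem from a serious one; only the patients' treatment histories can narrow it. I rate this as a worthwhile, inexpensive improvement rather than a flaw that invalidates the study, and hold it with low confidence as to its practical size.

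**What to change.** 1. From clinic records, extract each patient's last systemic psoriasis agent and its stop date, and report both by group.
2. Replace the unadjusted between-group test of change in PWV and AIx75 with a linear model (ANCOVA) containing group, the baseline value and recent systemic exposure (yes/no).
3. Pre-specify a sensitivity analysis, for both the within-group and the between-group change, limited to patients with no systemic psoriasis therapy in a stated window before baseline. The 3 months that the protocol already uses for TNF inhibitors could serve, as an analysis window only; the documents do not show that it suits other drugs. This step is needed because the covariate in step 2 does not correct the within-group change.
4. State whether ustekinumab counts as an IL23 inhibitor under the first exclusion.

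None of this changes eligibility, washout or treatment. The cost is two fields from existing records, one covariate and one extra analysis, and it remains feasible after enrolment if the records hold the data. The downside is that the restricted set is smaller and its intervals wider. If few patients in a group remain, that should be reported as a limit on what the comparison can show.
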